CanCope Micro-Randomized Trial Study Protocol and Statistical Analysis Plan

NCT05328362

10/01/2023

Methods

Study Design

The CanCope Study was a micro-randomized trial (MRT) conducted to gather evidence about the feasibility of a mobile intervention to reduce cannabis craving among young adults. The study duration was from August, 2021 to October, 2021. Each participant remained in the study for 29 days including the date of their enrollment.

Study Participants

Participants were recruited from advertisements on social targeting young adults who were interested in reducing their cannabis use and who resided in the United States. Participant screening, informed consent, and study surveys were all conducted electronically, with no staff contact. Interested individuals from the target population who saw the recruitment ads downloaded the MetricWire app by clicking a link (if the participant was already on their phone) or by scanning a QR code (if the participant was browsing on their computer). Assessment, randomization, and intervention content were delivered through a commercially available app (MetricWire). Upon downloading the app, interested individuals were prompted to enter their name and email address. After verifying their email address, participants were given a brief introduction to the study in the app and asked if they consented to be screened for eligibility to participate in the study. Consenting participants continued to complete the initial eligibility screening which asked about the participants' age, whether they were pregnant/breastfeeding, whether they were in treatment for substance use, assessed willingness and readiness to reduce their cannabis use, and gathered information about participant's substance use frequency over the past 30 days including cannabis use. People were excluded from participating if they were outside the ages of 19 - 25 years, pregnant or breastfeeding, currently receiving treatment for

substance use, or used cannabis fewer than 10 out of the past 30 days. Eligible participants were then given additional information about the study and asked if they consented to participate in the intervention phase. Consenting participants who completed the demographics and baseline surveys were enrolled. All enrolled participants automatically began the 28-day intervention period the day following the completion of their baseline survey. This study was approved by the Dartmouth College Institutional Review Board.

CanCope Intervention

The CanCope intervention was delivered through the MetricWire app, which participants downloaded onto their personal mobile phones. CanCope consisted of "push" interventions, comprised of messages sent by the MetricWire system. Messages were either a mindfulness-based strategy for coping with cannabis cravings, a distraction-based strategy for coping with cannabis cravings, a distraction-based strategy for coping with cannabis cravings, a distraction-based strategy for coping with cannabis cravings, or a control message thanking the participant for engaging in the study. A message was randomly delivered (or not delivered) according to a decision rule. All messages were created according to evidence-based interventions (Guarino et al., 2018; Witkiewitz et al., 2014).

Example mindfulness-based coping strategy: "You may be thinking 'I can't stand this,' or 'this is unbearable and not worth the effort.' Just notice these thoughts of distress then carry them away, letting them come and go. Remember, you can have whatever thoughts and feelings you have and still act differently than what you think or feel."

Example distraction-based coping strategy: "We can only pay attention to so many things at one time. To distract yourself from unpleasant thoughts, you can pay attention to your physical surroundings, or events or objects around you. For example, you might look around the room to find all the circular or rectangular objects and count them."

Study Procedure and Randomization

Baseline

The screening survey administered at baseline assessed participants' age, pregnancy or breastfeeding status, whether they were receiving counseling or treatment for substance use problems, and cannabis use in the past 30 days. Cannabis use in the past 30 days was measured using a scale from 0 to 30 days, where 0 = no days of cannabis use in the past 30 days (SAMHSA, 2015). If eligible based on the screening survey, participants self-reported gender identity, sexual orientation, race, and ethnicity.

Intervention

During the intervention, participants received five EMA push notifications via the study app daily at a set window to assess their cannabis craving level. Those who self-reported elevated cannabis craving (\geq 4 on a scale from 0 – 10 where 0 = no urge to use and 10 = extreme urge to use) received a second push notification prompting them to click on a new message. If they clicked on that new message, they were eligible for micro-randomization. The new message contained either one of the two intervention messages (mindfulness or distraction coping strategy) or a control message. Study participants received \$1 for each EMA completed, with an additional \$10 per week if they completed >80% of their EMA prompts for the week.

At each decision point, the randomization was independent of previous randomizations. During the 28-day intervention period, messages were randomized up to 140 (5x28) times for each participant. We used a probability of .66 for receiving a message and a probability of .34 for receiving a control message at each decision point when participants were available for the intervention.

Figure 1. Intervention flow

Outcomes and Measures

The aim of this study was to identify which strategies were most effective in helping participants cope with their cannabis cravings.

Proximal Outcome Measure

Cannabis craving has been positively correlated with cannabis use. Therefore, this study's primary proximal, or short-term, outcome was the effect of messaging on cannabis craving, determined by assessing the level of craving at the next EMA after the decision point for sending a coping strategy or control message.

Distal Outcome Measure

The distal, or long-term, exploratory outcome was the frequency of cannabis use over the past 30 days. The conceptual model underlying this MRT is that if the proposed intervention improves participants' ability to cope with cannabis cravings, they will be less likely to use cannabis. Given the exploratory nature of this objective, results are not presented for this outcome.

Statistical Analysis

We used a centered and weighted least squares (CWLS) method to analyze all available data (Boruvka et al., 2018; Klasnja et al., 2019; Qian et al., 2022). This method accommodates

within-participant correlation across time which results from the MRT design with decision points nested within participants. Furthermore, this method accounts for the endogeneity inherent in the MRT design due to the fact participant availability for intervention and covariates (e.g., pre-intervention craving level) are likely impacted by prior intervention. By capitalizing on the sequential randomization to estimate causal treatment effects, the CWLS method accounts for endogeneity in the data analyses (Klasnja et al., 2019; Qian et al., 2020).

We conducted a power analysis using the MRT sample size calculator to identify the needed sample size for 80% power to detect a small effect size of 0.2, assuming a 0.05 type 1 error rate, and 20% eligibility for randomization (3 out of 5 EMAs completed per day; craving level \geq 4 on 1 out of the 3 submitted EMAs; and clicking on the delivered message every time craving was elevated). To meet this assumption, the desired sample size was 47. To allow for 15% attrition defined by failure to complete any EMAs, we recruited 8 additional participants. **Results**

Study Participants

A total of 93 individuals downloaded the app which housed the intervention (MetricWire; www.metricwire.com). Of those, 74 individuals verified their email address used to register for the app and were assessed for eligibility to participate in the study. Of the 74 individuals assessed, 13 were ineligible because they met exclusion criteria: 4 did not complete the screening; 1 did not consent to be screened; 4 were not between the ages of 19 and 25 years; 1 was pregnant or breastfeeding; 1 was currently in treatment for a substance use disorder; and 3 did not use cannabis ≥10 out of the past 30 days. One person met two exclusion criteria and is reflected twice in the reason counts. Of the 61 individuals eligible to participate 8 did not enter the study: 1 did not complete the consent form; 1 did not consent to participate; 4 did not

complete the baseline assessments; and 2 did not complete any EMA. During the course of the study, 4 participants were lost to follow-up. We used all available data in the analyses, so all 53 participants who submitted at least one EMA during the course of the study are included in the analyses.

Outcomes

Decision Points, Participant Availability, and Message Delivered

For the 53 study participants, there were 140 possible decision points per person during the 28 days of the intervention period, for a total of 7420 possible person-decision points among all participants. Participants were eligible for the intervention during 1321 of the 7420 decision points (18%). A total of 406 mindfulness messages were delivered, 461 distraction messages, and 454 control messages when participants were eligible to be randomized to an intervention condition.

Effect of Coping Strategy Messages on Cannabis Craving in the Next EMA after a Decision Point

Our primary analysis showed that among all the decision points for which participants were eligible to receive an intervention throughout the 28-day intervention period, the average craving level after receiving a control message was 4.74 (SD = 2.82) and average craving level after receiving an intervention message was 4.63 (SD = 2.78). There was no statistically significant intervention effect (z = -0.54, p = .589).

References

- Guarino, H., Fong, C., Marsch, L. A., Acosta, M. C., Syckes, C., Moore, S. K., ... Rosenblum,
 A. (2018). Web-Based Cognitive Behavior Therapy for Chronic Pain Patients with
 Aberrant Drug-Related Behavior: Outcomes from a Randomized Controlled Trial. *Pain Med*, 19(12), 2423-2437. https://doi.org/10.1093/pm/pnx334
- Qian, T., Walton, A. E., Collins, L. M., Klasnja, P., Lanza, S. T., Nahum-Shani, I., . . . Murphy,
 S. A. (2022). The microrandomized trial for developing digital interventions:
 Experimental design and data analysis considerations. *Psychol Methods*.
 https://doi.org/10.1037/met0000283

SAMHSA. (2015). National Survey on Drug Use and Health (NSDUH).

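### The stated aim is to find which coping strategy works best, but the only analysis in the document pools mindfulness and distraction against control

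*Combined protocol and SAP*

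**What the plan says.** Outcomes and Measures gives the aim as "The aim of this study was to identify which strategies were most effective in helping participants cope with their cannabis cravings". The Intervention section describes three conditions: the message was "either one of the two intervention messages (mindfulness or distraction coping strategy) or a control message". Its probabilities have two levels only: "We used a probability of .66 for receiving a message and a probability of .34 for receiving a control message". The text does not say how the .66 was divided between the strategies. The primary proximal outcome is the effect of messaging on craving, "determined by assessing the level of craving at the next EMA after the decision point for sending a coping strategy or control message".

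The Statistical Analysis section names the CWLS method but no contrast or treatment coding. Its power calculation (effect 0.2, 80% power, alpha 0.05, 20% availability) does not name the comparison, and it concludes that "the desired sample size was 47".

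The results count deliveries by strategy: "A total of 406 mindfulness messages were delivered, 461 distraction messages, and 454 control messages". Craving is reported for two groups only, a control mean of 4.74 (SD 2.82) and, for either strategy, "average craving level after receiving an intervention message was 4.63 (SD = 2.78". One test follows, z = -0.54, p = .589.

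**The concern.** A comparison of any coping message with control estimates a weighted average of two strategy effects. It carries no information about the difference between them, so it cannot answer a question about which strategy is more effective, whether the result is null or positive. No contrast of mindfulness with control, distraction with control, or mindfulness with distraction is planned or reported in the document. The section explains why distal results are left out, but no reason is given for the missing strategy comparison.

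Two things are at stake. The document's own question goes unanswered although the randomised data to address it exist. And a reader may take the pooled null to mean that neither strategy works, which it does not show.

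**Working it through.** **1. The reported test is a pooled one.** The text does not use that word, but the figures leave no other natural reading.
- 406 + 461 + 454 = 1321, which is every eligible decision point.
- 406 + 461 = 867 coping messages, and 867/1321 = 65.6%. Control is 454/1321 = 34.4%. These match .66 and .34.
- z = -0.54 gives a two-sided p of .589, as reported.

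**2. What the pooled result leaves open.** This step assumes that the raw mean difference is close to the CWLS estimate.
- Difference: 4.63 - 4.74 = -0.11. Implied SE: 0.11/0.54 = 0.204.
- 95% CI: -0.11 ± 1.96 × 0.204 = -0.51 to 0.29. Rounding of the means and z moves the lower limit between -0.46 and -0.56.
- The pooled SD is about 2.79, so the lower limit is 0.509/2.79 = 0.18 SD if both strategies work equally.
- The -0.11 fits -0.11 for each strategy. It also fits zero for mindfulness with -0.11/(461/867) = -0.21 for distraction.
- If only distraction works, the lower limit corresponds to -0.509/(461/867) = -0.96 points (0.34 SD). If only mindfulness works, it is -0.509/(406/867) = -1.09 points (0.39 SD).

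**3. The planned sample size.** Assume an even .33/.33 split. Information per eligible decision point is:
- pooled: .66 × .34 = .2244
- one strategy versus control: .33 × .34/.67 = .1675
- mindfulness versus distraction: .33 × .33/.66 = .165

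The SE ratios to the pooled contrast are √(.2244/.1675) = 1.158 and √(.2244/.165) = 1.166.

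Noncentrality = N × 140 × .20 × information × d², referred to a noncentral F at alpha .05. The document does not state the time trend of the effect, so two models are shown: a constant effect (1 df, denominator N - 2) and a quadratic trend with a flat true effect (3 df, denominator N - 6). The pooled comparison needs 48 under the quadratic model, close to the stated 47, and 34 under the constant model.

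| Contrast | d | Noncentrality at N = 47 | Power, 3 df | Power, 1 df | N for 80% (3 df / 1 df) |
|---|---|---|---|---|---|
| Pooled versus control | 0.2 | 11.81 | .793 | .920 | 48 / 34 |
| One strategy versus control | 0.2 | 8.82 | .655 | .828 | 63 / 44 |
| Mindfulness versus distraction | 0.2 | 8.69 | .648 | .822 | 64 / 45 |
| Pooled, only one strategy at 0.2 | 0.1 | 2.95 | .249 | .391 | 178 / 127 |

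**4. Precision available now for strategy contrasts.**
- SE of the pooled difference if observations were independent: √(2.82²/454 + 2.78²/867) = 0.163. The reported test implies 0.204, a ratio of 1.253.
- Applying that ratio to 2.79 × √(1/n₁ + 1/n₂) gives about 0.239 (mindfulness versus control), 0.231 (distraction versus control) and 0.238 (mindfulness versus distraction).
- Multiplying by 2.80 gives differences detectable with 80% power of about 0.67, 0.65 and 0.67 points. The 95% CI half-widths are about 0.45 to 0.47.
- This treats every delivered message as having a next-EMA outcome, which is optimistic.

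**The case against.** The Study Design section gives feasibility as the purpose of the trial, and the primary outcome concerns messaging in general, so the primary outcome and the primary result agree. On that view one aim sentence is too broad, which is a wording gap and not a wrong analysis. The results also speak of a primary analysis, so strategy contrasts may have been run and left out of a short retrospective document. Figure 1, not seen here, may show the allocation split. Nowhere does the document say that neither strategy works. The one-strategy bounds sit at the edge of the interval and set the other effect to exactly zero. The power range straddles 80% and rests on an unstated trend. Finally, three unadjusted contrasts could invite selective ranking.

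Much of this stands as qualification. The pooled test is a proper primary analysis. The finding is limited to this document. The bounds show what the interval fails to exclude and are not estimates. The power figures do not settle whether the trial was large enough for strategy contrasts, and the mismatch does not depend on them. Multiplicity is a real cost: Bonferroni over three contrasts cuts planning power at N = 47 to between about 47% (3 df) and 68% (1 df). None of it withdraws the aim or supplies the missing contrast.

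**Conclusion.** The concern holds. The document states a strategy-level aim, randomises three conditions and then plans and reports nothing below the pooled comparison, so its own question is unanswered within it. The primary result is not in doubt, and the point is one that should be fixed.

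The mismatch follows from the text alone. Its size rests on assumptions: the interval and bounds need the raw difference to be close to the CWLS estimate, and the planning figures need the even split and one of the two trend models, neither of which is confirmed. On those terms the pooled null is compatible with a one-strategy reduction well above the 0.2 SD design effect. The pooled test would also have had only about 25% to 39% power if a single strategy had that design effect.

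**What to change.** Leave the pooled contrast as the primary result. Confirm the randomisation probability of each strategy. Then fit one CWLS model to the existing data with two treatment indicators, each centred at its actual probability. Report mindfulness versus control, distraction versus control, and mindfulness minus distraction with 95% CIs, labelled as added after the pooled result was known. Say whether the intervals are adjusted for three comparisons. A 2-df joint test may accompany them but is not confirmatory. State that the pooled null does not show which strategy works, or that neither does. If the contrasts are not added, restate the aim as any coping message versus control.

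The cost is one model and some wording. Pairwise standard errors are about 16% larger than the pooled one, so a non-significant strategy contrast may be inconclusive and should be read from its interval. Keeping the pooled test primary also protects power where both strategies work equally at 0.2: 92%, against 85% for the 2-df joint test (constant-effect model, N = 47).

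### Must the plan say whether the next-EMA outcome is the next scheduled or next submitted one, and add a check for unanswered outcomes?

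*Combined protocol and SAP*

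**What the plan says.** Under Proximal Outcome Measure, the primary outcome is the effect of messaging on craving, "determined by assessing the level of craving at the next EMA after the decision point for sending a coping strategy or control message". The Intervention section describes five daily prompts in a set window, but gives no window length, expiry time or maximum lag. Figure 1 (intervention flow) is not shown in the text reviewed and may carry timing detail.

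Statistical Analysis states: "We used a centered and weighted least squares (CWLS) method to analyze all available data". It says the method handles within-participant correlation and the fact that "participant availability for intervention and covariates (e.g., pre-intervention craving level) are likely impacted by prior intervention". It does not mention missing outcomes. The power calculation in the same section assumes "3 out of 5 EMAs completed per day".

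Participants were paid $1 per EMA, plus $10 a week "if they completed >80% of their EMA prompts for the week". Payment did not depend on which message was drawn.

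In the Results, Study Participants reports that "all 53 participants who submitted at least one EMA during the course of the study are included in the analyses", and also: "During the course of the study, 4 participants were lost to follow-up". The Outcomes section counts 406 mindfulness, 461 distraction and 454 control messages. It gives the primary result as mean craving "among all the decision points for which participants were eligible to receive an intervention": 4.74 (SD 2.82) after control and 4.63 (SD 2.78) after an intervention message, z = -0.54, p = .589. The number of those points with an observed outcome is not given.

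**The concern.** The two readings are different analyses. If the outcome is the next scheduled prompt, each unanswered prompt is a missing outcome. If it is the next submitted EMA, few outcomes are missing but the lag varies. At the power calculation's 60% completion, with independent responses, 40% of outcomes would come from a later prompt than the next one, and 0.4 x 0.4 = 16% from the third or later.

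Answering follows randomization, so neither randomization nor the stated protections of the centered and weighted method cover selective non-response. The 53 participants are people with at least one EMA, whereas an outcome needs a later answered EMA. If answering depended jointly on the message and on next craving (or its causes), the observed contrast could be biased. At stake would be the accuracy of a 0.11-point difference and its interval and, with a large enough shift, the non-significant verdict.

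**Working it through.** **Reported figures.** 406 + 461 + 454 = 1,321, of which 867 are intervention and 454 control; 1,321/7,420 = 17.8%, reported as 18%. A two-sided p for z = -0.54 is .589, as reported.

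**Precision.** Assume the model estimate equals the raw difference, 4.63 - 4.74 = -0.11.

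- SE = 0.11/0.54 = 0.204 (0.18 to 0.22 allowing for rounding).
- 95% CI = -0.11 ± 1.96 x 0.204 = -0.51 to 0.29.
- Shift needed for significance: 0.40 - 0.11 = 0.29 towards benefit, or 0.40 + 0.11 = 0.51 towards harm.

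**Can z reveal how many outcomes were used?** The simple two-sample SE is sqrt(2.82²/454 + 2.78²/867) = 0.163 with all outcomes observed, and 0.163/sqrt(0.6) = 0.210 with 60% observed. The implied 0.204 lies between them, but clustering and weighting also affect it. So z does not settle the count.

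**Size of a possible shift.** Shift = (share missing x missed-minus-answered craving gap) in intervention, minus the same in control. The documents give neither the shares nor the gaps, so the values below are assumptions. Response is taken as equal in both arms, with a gap that differs between arms by one point.

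| Reading | Share missing | Shift | Gap difference needed for a 0.29 shift |
|---|---|---|---|
| Next scheduled, 90% response | 0.10 | 0.10 | 2.9 points |
| Next scheduled, 80% response | 0.20 | 0.20 | 1.4 points |
| Next scheduled, 60% response | 0.40 | 0.40 | 0.7 points |
| Next submitted, upper bound | 53/1,321 = 0.040 | 0.04 | 7.2 points |

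A shift of 0.20 gives z = -0.31/0.204 = -1.52 or 0.09/0.204 = +0.44. A shift of 0.40 gives z = -2.50 or +1.42.

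**Why 53 is the bound under next submitted.** With no maximum lag, an outcome is missing only if the decision point was that participant's last submitted EMA, so at most one per person. If all 53 fell in one arm, a one-point gap there would shift the contrast by 53/867 = 0.06 (intervention) or 53/454 = 0.12 (control). If a last EMA is no more likely than any other to be a decision point, the expected number is 53 x 1,321/(7,420 x response) = 15.7, 11.8 or 10.5 at 60%, 80% or 90% response. That is about 0.8% to 1.2% of outcomes.

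**Would response weighting help?** A simulation of 2 million points with no true effect assumed the following:

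- triggering craving normal (mean 6.3, SD 1.8), rounded and clipped to 4-10;
- next craving 0-10 with mean 4.7, SD 2.6 and correlation 0.50 with triggering craving;
- message probability .66;
- logistic response falling by 0.05, 0.10, 0.20 or 0.35 logits per craving point.

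| Response depends on | Observed-only bias | After weighting on arm and triggering craving |
|---|---|---|
| Next craving, same slope, 83% v 75% answered | 0.03, 0.05, 0.11, 0.17 | 0.02, 0.04, 0.08, 0.13 |
| Next craving in control only, 80% answered | 0.07, 0.14, 0.27, 0.44 | 0.05, 0.10, 0.20, 0.34 |
| Triggering craving in control only, 80% answered | 0.02, 0.04, 0.09, 0.15 | 0.00 |
| Same slope and 80% in both arms | 0.00 | not needed |

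Weighting removes bias that runs through triggering craving. When answering depends on next craving itself, it removes only about a quarter (0.11 to 0.08; 0.27 to 0.20).

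**Would a shift analysis help?** With 20% missing and shifts of 2 points in opposite directions in the two arms, the contrast moves by 0.20 x 4 = 0.80, and z runs from (-0.11 - 0.80)/0.204 = -4.5 to (-0.11 + 0.80)/0.204 = +3.4. That range includes almost any verdict.

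**The case for a change.** The strongest case for a change is that the definition really is absent from the visible text. The statement that all eligible decision points were used describes a population and is not a count. One sentence and a small table of observed outcomes and lag by arm would cost almost nothing and might close the question. A modest assumed mechanism also produces shifts as large as the whole reported difference. With 60% response, the only completion figure in the documents, a one-point arm difference in the gap gives 0.40, which exceeds the 0.29 threshold towards benefit. It would therefore be wrong to say that the null verdict is safe under every reading.

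All of that stands as a description of what is unreported, but it does not show a fault in the analysis. The 60% is a power input for all prompts, whereas every randomized point followed an answered EMA and a click, whichever message was drawn, so it is probably a low case here. The large shifts need the missed-minus-answered gap to differ by a full point between arms. With equal response and a common gap, the shift is zero. Restricting the analysis to answers from the next scheduled prompt, if the next submitted EMA was used, would select on a post-randomization response and so introduce the problem it was meant to test.

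**Conclusion.** No change to the plan follows. This is missing detail that the analysts must have resolved in order to fit the model. Writing down the definition and the counts would be a courtesy to the reader and would leave the primary estimate and method unchanged. The trial is complete, and the documents contain no evidence that answering or lag differed by message.

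Under the next-submitted reading, at most 4.0% of outcomes are missing and little is at stake; no bias figure is claimed for lag. Under the next-scheduled reading, the missing share is unknown, and the result is robust to shifts below 0.29 towards benefit or 0.51 towards harm, but not beyond. These limits assume that the model estimate equals the raw difference of -0.11; the response rates, gaps and slopes are assumed ranges, not estimates for this trial. The extra analyses would be post hoc, and they would correct only for measured predictors of answering, give a range too wide to be informative, or add selection of their own.
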